### **3.2 Clinical Safety Evaluations**

Clinical safety evaluations will be performed to ensure that the subjects meet the requirements of the study and to monitor subject safety. These will include physical examinations, vital signs, ECG, clinical laboratory tests (clinical chemistry, hematology, urinalysis, and serology), urine drug screens, breath alcohol tests, and pregnancy tests (females only) at designated time points during the study. AEs will be monitored and recorded from the time of the first product use (VERVE® product trial at Check-in) through the End-of-Study (or Early Termination).

For all scheduled clinical laboratory tests, approximately 30 mL of blood will be collected from each subject.

## **4 SUBJECT SELECTION**

The following inclusion and exclusion criteria must be satisfied.

### **4.1 Inclusion Criteria**

- 4.1.1. Voluntary consent to participate in this study documented on the signed informed consent form (ICF).
- 4.1.2. Healthy adult males and females 21 to 65 years of age, inclusive, at Screening.
- 4.1.3. Smoking history of an average of at least 10 but no more than 30 factory manufactured combustible cigarettes daily for at least 1 year prior to Screening. Brief periods (i.e., up to 7 consecutive days) of non-smoking during the 3 months prior to Screening (e.g., due to illness or participation in a study where smoking was prohibited) will be permitted.
- 4.1.4. Positive urine cotinine ( $\geq 500$  ng/mL) at Screening.
- 4.1.5. Female subjects who are heterosexually active and of childbearing potential (e.g., neither surgically sterile at least 6 months prior to Check-in nor postmenopausal with amenorrhea for at least 1 year prior to Check-in with FSH levels consistent with postmenopausal status) must have been using one of the following forms of contraception for the time period indicated and agree to continue using it through completion of the study:
  - hormonal (e.g., oral, vaginal ring, transdermal patch, implant, injection) consistently for at least 3 months prior to Check-in,

- double barrier (i.e., condom with spermicide or diaphragm with spermicide) consistently for at least 4 weeks prior to Check-in,
- intrauterine device for at least 4 months prior to Check-in,
- exclusive partner who has been vasectomized for at least 6 months (inclusive) prior to Check-in.

Female subjects of childbearing potential who are not currently engaging in heterosexual intercourse must agree to use one of the above methods of birth control through completion of study, in the event that they have heterosexual intercourse during the course of the study.

4.1.6. Female subjects who are of non-childbearing potential must have undergone one of the following sterilization procedures at least 6 months prior to Check-in:

- hysteroscopic sterilization (including Essure® or similar nonsurgical sterilization procedures);
- bilateral tubal ligation or bilateral salpingectomy;
- hysterectomy;
- bilateral oophorectomy;

Or be postmenopausal with amenorrhea for at least 1 year prior to Check-in and have FSH levels consistent with postmenopausal status.

4.1.7. Willing to comply with the requirements of the study.

4.1.8. Willing to use all four VERVE® test products after products trial at Check-in.

4.1.9. Willing and able to abstain from cigarettes from Day 1 through the End of the study.

## 4.2 Exclusion Criteria

Subjects will be excluded from the study if there is evidence of any of the following criteria at Screening, Check-in, or prior to randomization, as appropriate.

4.2.1. Use of any type of tobacco- or nicotine-containing products other than manufactured cigarettes (e.g., e-vapor products, roll-your-own cigarettes, bidis, snuff, nicotine inhaler, pipe, cigar, chewing tobacco, nicotine patch, nicotine spray, nicotine lozenge, or nicotine gum) in the 7 days prior to Check-in

4.2.2. Self-reported puffers (i.e., adult smokers who draw smoke from the cigarette into the mouth and throat but do not inhale).

4.2.3. Planning to quit smoking in the next 30 days (from Screening visit).

- 4.2.4. History or presence of clinically significant gastrointestinal, renal, hepatic, neurologic, hematologic, endocrine, oncologic, urologic, existing respiratory diseases, immunologic, psychiatric, lymphatic, or cardiovascular disease, or any other condition that, in the opinion of the Investigator, would jeopardize the safety of the subject or impact the validity of the study results.
- 4.2.5. Clinically significant abnormal findings on the vital signs, physical examination, medical history, ECG, or clinical laboratory results, in the opinion of the Investigator.
- 4.2.6. Positive test for human immunodeficiency virus (HIV), hepatitis B surface antigen (HBsAg), or hepatitis C virus (HCV) at Screening.
- 4.2.7. History or presence of any type of malignant tumors.
- 4.2.8. Current evidence or any history of congestive heart failure.
- 4.2.9. Diabetes mellitus (fasting glucose  $\geq 126$  mg/L [7 mmol/L]) that is not controlled by diet/exercise alone, in the opinion of the Investigator.
- 4.2.10. An acute illness (e.g., upper respiratory infection, viral infection) requiring treatment with prescribed medicines within 2 weeks prior to Check-in.
- 4.2.11. Dentition that prevents subjects from chewing VERVE® products.
- 4.2.12. Allergic to or cannot tolerate mint flavoring agents or phenylalanine.
- 4.2.13. Any planned surgery from the time of Screening through the End-of-Study.
- 4.2.14. History of drug or alcohol abuse within 24 months prior to Check-in.
- 4.2.15. Fever (i.e., body temperature  $> 100.5^{\circ}\text{F}$ ) at Screening or Check-in. One recheck may be performed at the Investigator's discretion.
- 4.2.16. Body mass index (BMI) greater than  $40.0 \text{ kg/m}^2$  or less than  $18.0 \text{ kg/m}^2$  at Screening.
- 4.2.17. Systolic blood pressure  $> 150 \text{ mmHg}$  and/or diastolic blood pressure  $> 90 \text{ mmHg}$  at Screening or Check-in, measured after being seated for at least 10 minutes. One recheck may be performed at the Investigator's discretion.
- 4.2.18. Clinically significant ECG abnormalities, in the opinion of the Investigator.
- 4.2.19. Estimated creatinine clearance (by Cockcroft-Gault equation)  $< 80 \text{ mL/minute}$  at Screening.
- 4.2.20. Serum alanine aminotransferase (ALT)  $\geq 1.5$  times the upper limit of normal and/or aspartate aminotransferase (AST)  $\geq 1.5$  times the upper limit of normal at Screening.
- 4.2.21. Positive screen for alcohol (breath) or any of the following drugs of abuse (urine), regardless of the reason of use: amphetamines,

methamphetamines, opiates, cannabinoids, or cocaine at Screening or Check-in.

- 4.2.22. Female subjects who are pregnant (positive serum pregnancy test at Screening or urine pregnancy test at Check-in), lactating, or intend to become pregnant from Screening through the End-of-Study.
- 4.2.23. Use of prescription or over-the-counter bronchodilator medication (e.g., inhaled or oral  $\beta$ -agonists) within 12 months prior to Check-in.
- 4.2.24. Use of medications or foods known or are suspected to interact with cytochrome P450 2A6 (including, but not limited to, amiodarone, amlodipine, amobarbital, buprenorphine, clofibrate, clotrimazole, desipramine, disulfiram, entacapone, fenofibrate, isoniazid, grapefruit, ketoconazole, letrozole, methimazole, methoxsalen, metyrapone, miconazole, modafinil, orphenadrine, pentobarbital, phenobarbital, pilocarpine, primidone, propoxyphene, quinidine, rifampicin, rifampin, secobarbital, selegiline, sulconazole, tioconazole, tranylcypromine) within 14 days or 5 half-lives of the drug, whichever is longer, prior to Check-in or during the study.
- 4.2.25. Use of antibiotic treatment within 2 weeks prior to Check-in.
- 4.2.26. Plasma donation within 7 days prior to Check-in.
- 4.2.27. Donation of blood or blood products (with the exception of plasma as noted above), had significant blood loss, or received whole blood or a blood product transfusion within 56 days prior to Check-in.
- 4.2.28. Participation in a previous clinical study for an investigational drug, device, biologic, or for a tobacco product within 30 days prior to Check-in.
- 4.2.29. Participation in two or more ALCS studies within the past 12-month period prior to Check-in.
- 4.2.30. Subject or a first-degree relative (i.e., parent, sibling, child, spouse/partner) is a current or former employee of the tobacco industry or a named party or class representative in litigation with any tobacco company.
- 4.2.31. Subject or a first-degree relative (i.e., parent, sibling, child, spouse/partner) is a current employee of the study site.

### **4.3      Restrictions**

- 4.3.1. No tobacco- or nicotine-containing product use from Day 1 until the End-of-Study except per protocol except at the designated time when only the study products or subjects' OB cigarettes are allowed.
- 4.3.2. No foods or beverages containing alcohol for 48 hours prior to Screening, Check-in or during confinement.

- 4.3.3. No broiled or pan-fried meat, pre-cooked meats (e.g., tuna, ham, corned beef, smoked lunchmeats), bacon, or sausage for 48 hours prior to Check-in or during confinement.
- 4.3.4. Caffeinated beverages (up to 1 cup per meal) may be served during confinement.
- 4.3.5. No strenuous exercise for 48 hours prior to Check-in or during confinement.

#### **4.4 Medications**

Any concomitant medications taken from 30 days prior to Screening through the End-of-Study (or upon early termination) will be recorded.

Prohibited medications are included in the exclusion criteria.

Stable doses (i.e., no dosage adjustments within 30 days prior to Screening) of prescription or over-the-counter medications required to treat an Investigator-approved disease or condition are permitted at the discretion of the Investigator. Hormonal contraceptives (e.g., oral, vaginal ring, transdermal patch, implant, injection) and hormonal replacement therapy are permitted. Occasional use of over-the-counter analgesics (e.g., acetaminophen, ibuprofen), antihistamines, and nasal decongestants are permitted as needed to treat AEs experienced by subjects at the discretion of the Investigator. Exceptions may be permitted at the discretion of the Investigator in consultation with the Sponsor, providing the medication in question would have no impact on the study. Any exceptions will be documented. Note that some decongestants might cause a positive urine drug screen result and therefore their use should be discouraged within 5 - 7 days of those tests.

### **5 SCREENING**

The Investigator or his/her designee must perform the following procedures within 28 days prior to Day -3 (Check-in). Tobacco cessation information (details in [Section 7.11](#)) will also be provided during this time.

#### **5.1 Informed Consent**

All prospective subjects will have the study explained by the Investigator or his/her designee.

All prospective subjects will be required to read, sign, and date the study ICF prior to any Screening/study procedures being performed. Written acknowledgment of the receipt of the full informed consent and the subject's freely tendered offer to participate will be obtained from each subject in the study and documented in the source documents. Each subject will receive a signed and dated copy of the ICF.

## **5.2 Medical History/Demographic Data/Record of Concomitant Medication**

Medical history and demographic data, including name, sex, age (each subject must show proof of age with government-issued identification (ID) [e.g., driver's license]), race, ethnicity, address, social security number or tax identification number, phone number, will be recorded for each subject.

Any concomitant medications taken from 30 days prior to Screening through the End-of-Study (or upon Early Termination) will be recorded.

## **5.3 Review Inclusion/Exclusion Criteria**

Site staff will confirm that the inclusion and exclusion criteria have been met prior to randomization. Subjects who do not meet the inclusion/exclusion criteria will be considered screen failures; data to be captured will include subject demographics and the reason(s) for screen failure.

## **5.4 Tobacco/Nicotine Product Use History**

Subjects will be required to report previous tobacco-product and nicotine-product use histories to satisfy the study inclusion and exclusion criteria. Smoking history must include usual number of cigarettes smoked per day and the number of years the subject has smoked.

The following characteristics of the OB cigarettes used will be documented: brand, brand style, flavor, and cigarette size. The average number of CPD (single number, not a range) will also be documented.

## **5.5 Physical Examination**

5.5.1. Height (cm) and weight (kg) in indoor clothing without shoes. BMI will be calculated as weight (kg)/height ( $m^2$ ).

5.5.2. Vital signs (respiratory rate, pulse rate, blood pressure, and body temperature) in the sitting position after at least 10 minutes of rest (with the exception of body temperature) and at least 15 minutes after the last cigarette smoked or VERVE® product used. One recheck of vital sign(s) may be performed at the Investigator's discretion.

5.5.3. General physical examination with observations and questioning by the Investigator or his/her designee.

5.5.4. 12-lead ECG in the supine position after at least 10 minutes of rest and at least 15 minutes after the last nicotine-containing product used. The QT interval corrected using the Bazett's formula will be recorded.

## **5.6 Clinical Laboratory Tests**

All clinical laboratory tests will be conducted by a laboratory accredited by Centers for Medicare and Medicaid Services (Clinical Laboratory Improvement Amendments of 1988 [CLIA-88]) or at the clinic study site using CLIA-waived kits or procedures. Values for the laboratory parameters are to be within the laboratory normal ranges or deemed not clinically significant in the opinion of the Investigator or his/her designee. One recheck may be performed at the Investigator's discretion for all clinical laboratory tests except for the urine drug screen, breath alcohol test, and urine cotinine.

- 5.6.1. Hematology, consisting of hemoglobin, hematocrit, red blood cell (RBC), white blood cell (WBC) with differential, and platelet count.
- 5.6.2. Clinical chemistry (after fasting for at least 8 hours; fasting requirements may be waived in the case of rechecks, as appropriate), consisting of sodium, potassium, chloride, bicarbonate, ALT, AST, blood urea nitrogen, alkaline phosphatase, total bilirubin, glucose, creatinine (at Screening, creatinine clearance will be calculated using Cockcroft-Gault formula), total protein, uric acid, and albumin.
- 5.6.3. Routine clinical urinalysis consisting of bilirubin, blood, glucose, ketones, leukocyte esterase, nitrite, pH, protein, specific gravity, and urobilinogen will be evaluated. Microscopic examination will be conducted if protein, leukocyte esterase, nitrite and/or blood are detected. Microscopic analysis will include RBC, WBC, casts, and bacteria.
- 5.6.4. Serology test for HIV, HBsAg, and HCV.
- 5.6.5. Urine cotinine; a positive quantitative test ( $\geq 500$  ng/mL) will be required for participation in the study.
- 5.6.6. Urine screen for amphetamines, methamphetamines, opiates, cannabinoids, and cocaine and breath test for alcohol. Subjects who test positive for alcohol and/or any of the drugs listed will be considered screen failures and will not complete the remaining screening assessments at this visit (with the exception of the Demographics and Tobacco/Nicotine Product Use History questionnaire).
- 5.6.7. Serum (at Screening) and Urine (at Check-in) pregnancy test for all females and serum FSH test for females reporting to be postmenopausal to confirm postmenopausal status.

## **5.7 Product Trial**

Subjects will have the opportunity to try both VERVE® Discs and VERVE® Chews following completion of check-in procedures on Day -3. Subjects will engage in a brief product trial with each flavor of VERVE® Chews (two flavors

[blue mint and green mint]) and VERVE® Discs (two flavors [blue mint and green mint]) (i.e., *ad libitum* use for 10 minutes each) to get accustomed to using the products. Trial of each flavor of VERVE® Chews or VERVE® Discs product will be separated by approximately 30 minutes (from the start of each product trial). Subjects who are unwilling to use and/or cannot tolerate all four VERVE® products will not continue in the study.

## 5.8 Fagerström Test for Cigarette Dependence (FTCD)

Subjects will complete the FTCD questionnaire ([Appendix 1](#)).

# 6 MATERIALS

## 6.1 Study Products

- Product A: Subject's OB Cigarette (Reference Product)
- Product B: Oral tobacco-derived nicotine chews marketed as VERVE® Discs Blue Mint (~1.5 mg nicotine/piece) (Test Product)
- Product C: Oral tobacco-derived nicotine chews marketed as VERVE® Discs Green Mint (~1.5 mg nicotine/piece) (Test Product)
- Product D: Oral tobacco-derived nicotine chews marketed as VERVE® Chews Blue Mint (~1.5 mg nicotine/piece) (Test Product)
- Product E: Oral tobacco-derived nicotine chews marketed as VERVE® Chews Green Mint (~1.5 mg nicotine/piece) (Test Product)

## 6.2 Study Materials Accountability, Storage, and Preparation

All study products will be provided by the Sponsor. The site staff will coordinate shipping of all study products from the Sponsor. The study staff will document the date each shipment was received and recorded in the inventory records. The study staff will document and reconcile the total number of study products shipped to the site, the total number of study products used during the study, and the total number of unused study products remaining at the end of clinical conduct.

The site pharmacy will retain and store 2 packages (16 discs per package) of each flavor VERVE® Discs product and 3 packs (12 pieces per pack) of each flavor VERVE® Chews products at the site until finalization of the final study report.

All study products will be stored in a locked, limited-access area in the clinic and kept at controlled room temperature (defined as 20° - 25°C [68° - 77°F], with excursions permitted to 15° - 30°C [59° - 86°F]).

All subjects will be required to provide a sufficient supply of their OB combustible cigarettes to the study site for use from Check-in through Day 7 (10 days) in case they are randomized to continue smoking their OB cigarettes. This supply will be calculated from the number of CPD reported at Screening plus

an additional 20% rounded up to the next pack. For example, a subject reporting to smoke 15 cigarettes per day would bring nine packs (15 cigarettes per day x 10 days = 150 cigarettes + an additional 30 cigarettes = 180 cigarettes total [9 packs]). The clinical site will purchase additional cigarettes if subjects run out of cigarettes during the study.

Study products for dispensing to subjects will be prepared each day. Individual study product dispensing records will be maintained by the site pharmacy for each subject.

Individual study product dispensing records will be maintained by the site for each subject and must include the date and time that each cigarette and VERVE® product was dispensed and each cigarette butt and VERVE® product was returned by each subject (subjects will be requested to return cigarette butts and used VERVE® products as soon as product use is completed). Site staff will reconcile the logs against the returned cigarette butts and VERVE® products prior to discarding.

Unused VERVE® products will be destroyed by the site or returned to Sponsor at the direction of the Sponsor after a full accounting has been performed by the monitor. Unused OB cigarettes will be returned to the subjects at discharge or upon early withdrawal according to the site's standard practices. All returns or destruction of study products will be documented.

## 7 STUDY CONDUCT

Subjects meeting all inclusion criteria and none of the exclusion criteria will check-in to the study site on Day -3 to undergo the procedures described below.

### 7.1 Check-in Procedures (Day -3)

- 7.1.1. Brief written assessment (medical/medication questionnaire) to affirm that the inclusion and exclusion criteria/restrictions have not been violated since the Screening visit.
- 7.1.2. Symptom-driven physical examination.
- 7.1.3. Vital signs (respiratory rate, pulse rate, blood pressure, and body temperature) to be performed in the sitting position after at least 10 minutes of rest (with the exception of body temperature) and at least 15 minutes after the last cigarette smoked. One recheck of vital sign(s) may be performed at the Investigator's discretion.
- 7.1.4. Product trial of VERVE® Discs and Chews products
- 7.1.5. Documentation of subject's willingness to use the VERVE® products in the study and flavor preference.
- 7.1.6. *Ad libitum* use of OB cigarette and documentation of CPD.

- 7.1.7. Urine pregnancy test for females.
- 7.1.8. Urine sample for drugs of abuse (amphetamines, methamphetamines, opiates, cannabinoids, and cocaine) screen.
- 7.1.9. Breath alcohol test.
- 7.1.10. Review of concomitant medications.
- 7.1.11. Review of AEs

## **7.2 Subject Confinement**

The subjects will be admitted to the study unit on Day -3 at a time designated by the clinic site and will remain in the clinic until completion of all study events on Study Day 8 or upon early termination.

## **7.3 Meal Schedule/Dietary Considerations**

Standard meals and snacks will be served at appropriate times as determined by the clinic during confinement. Meals each day should be similar in caloric content. Meal times will be documented.

A standardized diet (*i.e.*, low mutagenicity) designed by a dietitian to minimize possible confounding influences for biomarkers assessed will be used. The following will not be permitted: broiled or pan-fried meat, pre-cooked meats (*e.g.*, tuna, ham, corned beef, smoked lunchmeats), bacon, and sausage. These specially-designed meals will be served throughout the study according to a meal plan at the same approximate time throughout the study:

The same menu and approximate meal schedule will be administered uniformly to all subjects in all groups. The meal menu for Days -2, 4 and 6 will be the same and the meal menu for Days -1, 5 and 7 will be the same.

Consumption of alcoholic beverages will not be permitted during the study.

Water will be provided as desired during the study, and subjects will be encouraged to maintain their usual hydration habits.

## **7.4 Blinding**

This will be an open-label study.

## **7.5 Subject Randomization**

Subjects will be randomized into 6 groups (Groups 1 to 6) using an (Interactive Web Response System (IWRS). The randomization process may be completed on Day -1 as necessary to allow enough time to prepare the randomized products for use on Day 1.

Each subject will be assigned to a study group by the IWRS. Groups will be stratified by gender (male or female, no more than 60% of either gender) and CPD.

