## 7.3 Statistical Analyses

### 7.3.1 Primary Endpoint Analysis

A linear mixed model for repeated measures (MMRM) analysis will be used for comparing each test group (Groups 2-5) to the control group (Group 1 and Group 6) in the primary endpoint (24-hour total urinary NNAL (mg/24 hours) excreted on Day 7). In the model, study group, study day, and study group by study day interaction, and gender are the fixed effect factors. The baseline value of the response biomarker is the covariate. A restricted maximum likelihood estimation method will be applied and several covariance structures will be tried. Five candidate covariance structures will be considered: compound symmetry, 1st order autoregressive, 1st order autoregressive with a random subject effect, unstructured and Toeplitz. The most appropriate covariance structure will be determined based on the AIC criteria (the covariance structure with the smallest AIC will be chosen). The least-square mean, 95% confidence interval and p-value will be provided for the study groups. The least-square mean difference, 95% confidence interval and p-value will be provided for the study group comparisons. Pairwise comparisons (Group 2 vs. Group 1, Group 3 vs. Group 1, Group 4 vs. Group 1, Group 5 vs. Group 1, Group 2 vs. Group 6, Group 3 vs. Group 6, Group 4 vs. Group 6, and Group 5 vs. Group 6,) will be performed using a Dunnett's test at a 2-sided significance level of 0.05 to adjust for multiplicity. Group 1 & 6 will be considered as the control groups. The test is for each of the other groups to compare with the control groups. The analysis will be conducted on the mITT and PP datasets.

The following SAS codes will be used to perform the analysis.

```
Proc mixed data=<>;
Class subject gender group day;
Model response = gender group day group*day baseline/ddfm=kr;
Repeated day/type=<type> subject=subject;
LSmeans group*day/CL alpha=0.05 pdiff dunnett ('1'*Day 7, '6'*Day 7);
```

Run;

Note: This model will include both the Day 7 value (primary endpoint) and interim time points (Day 5, secondary endpoint). The above analysis will also output the residual diagnosis to check for normality and to identify outliers).

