## **7.3.2 Secondary Endpoint Analysis**

The same statistical analysis model defined in the primary analysis Section 7.3.1 will also be used to make same comparisons as the primary endpoint (i.e. total NNAL on Day 7) for the secondary biomarker endpoints listed in Section 2.4.

These analyses will be conducted on the mITT and PP datasets.

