## **7.3.3 Subjective Effects**

Similar statistical comparison analysis (defined in 7.3.1) will be preformed on QSU-brief change from pre-use score and mCEQ original scores (mCEQ-C, among Group 1, 2, and 3; mCEQ-V, among Groups 2, 3, 4, and 5). The comparisons interested for QSU-brief will be the test groups (Groups 2-5) versus the continue smoking group (Group 1) and test groups (Groups 2-5) versus the tobacco cessation Group. The comparisons interested for mCEQ-C will be the dual use groups (Groups 2-3) versus the continue smoking group (Group 1). The comparisons interested for mCEQ-V will be the dual use groups (Groups 2-3) versus the exclusive use group (Groups 4 -5) [i.e. Group 2 vs Group 4 and Group 3 vs Group 5].

This analysis will be conducted on the mITT datasets. No multiple adjustment will be performed for subject effect scores.

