#### 7.3.4.2 Handling of Missing Data

Two methods (last observation carried forward and multiple imputation) will be tested for the handling of missing data for the primary endpoint if the percentage of missing data is larger than 5% in the mITT population. For all other analyses, data will not be imputed. Baseline is not expected to be missing for the mITT population.

Multiple imputation will be conducted to impute the missing data values for the primary endpoints (24-hour total urinary NNAL (ng/24 hours) excreted on Day 7). The imputation starts with using SAS procedure Proc MI to generate (n=m) completed data sets. Then each data set will be analyzed with SAS procedure Proc Mixed to generate m point estimates and standard errors for the model parameters. Finally, SAS procedure Proc Mianlyze will be used to combine the estimation results

The Following SAS codes will be used for imputation and analysis.

- 1) use PROC MI to impute the missing data;

```
proc mi data=... seed=... nimpute=200 out=miout noprint;  
  mcmc;  
  var biomarker_baseline biomarker_Day5 biomarker_Day7 ;  
  run;
```

- 2) use PROC MIXED to model the multiple imputed datasets:

```
proc mixed data=miout order=internal ;  
  where day=7;  
  by _imputation_;  
  class subject gender group ;  
  model biomarker = gender group baseline/ddfm=kr;  
  lsmeans group / alpha=0.05 CL pdiff;  
  ods output lsmeans=lsmnout;  
  ods output diffs=diff;  
  run;
```

- 3) use PROC MIANALYZE to generate the int (lsmnoutmi, diffmi) from the multiple estimates (lsmnout, diff).

```
proc sort data=lsmnout;by group _imputation_;run;  
proc mianalyze data=lsmnout alpha=0.05;
```

```
by group ;
model effects group;
  ods output ParameterEstimates=lsmnoutmi;
  stderr stderr;
run;

proc sort data=diff,by group _imputation_;run;
proc mianalyze data=diff alpha=0.05;
  by group ;
  model effects group;
  ods output ParameterEstimates=diffmi;
  stderr stderr;
run;
```

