	CV (%)	XX.X	XX.X	XX.X	XX.X	XX.X	XX.X
	SEM	X.XX	X.XX	X.XX	X.XX	X.XX	X.XX
	Minimum	XX	XX	XX	XX	XX	XX
	Median	X.X	X.X	X.X	X.X	X.X	X.X
	Maximum	XX	XX	XX	XX	XX	XX
	95% CI	XX.X, XX.X					
7	<same as above>						

Group X = <description of groups>

Program: /CAXXXX/sas\_prg/pksas/PROGRAMNAME.SAS DDMMYYYY HH:MM

**Note: Statistical summary tables 14.2.1.1.5-6.1, 14.2.1.2.5-6.1, 14.2.1.3.5-6.1, 14.2.1.4.5-6.1, 14.2.1.5.5-6.1, 14.2.1.6.5-6.1, 14.2.1.7.5-6.1, 14.2.1.8.5-6.1, 14.2.1.9.5-6.1, 14.2.1.10.5-6.1, 14.2.1.11.5-6.1, 14.2.1.12.5-6.1, 14.2.1.13.5-6.1, 14.2.1.14.5-6.1, 14.2.1.15.5-6.1, 14.2.1.16.5-6.1, 14.2.1.17.5-6.1, 14.2.1.18.5-6.1, 14.2.1.19.5-6.1, and 14.2.1.20.4-5.1 will have the following format:**

Page 1 of X

Table 14.2.1.1.5.1 Statistical Summary of <Matrix> <Biomarker> (<Units>) by Study Group and Study Day (mITT Population)

Group	Study Day	n	LS Mean	XX% Confidence Interval	p-value
1	5	XX	X.XX	XX.XX - XXX.XX	X.XXXX
	7	XX	X.XX	XX.XX - XXX.XX	X.XXXX
2	5	XX	X.XX	XX.XX - XXX.XX	X.XXXX
	7	XX	X.XX	XX.XX - XXX.XX	X.XXXX
3	5	XX	X.XX	XX.XX - XXX.XX	X.XXXX
	7	XX	X.XX	XX.XX - XXX.XX	X.XXXX
4	5	XX	X.XX	XX.XX - XXX.XX	X.XXXX
	7	XX	X.XX	XX.XX - XXX.XX	X.XXXX
5	5	XX	X.XX	XX.XX - XXX.XX	X.XXXX
	7	XX	X.XX	XX.XX - XXX.XX	X.XXXX
6	5	XX	X.XX	XX.XX - XXX.XX	X.XXXX
	7	XX	X.XX	XX.XX - XXX.XX	X.XXXX

Note: The mixed model for repeated measures includes study group, study day, study group by study visit interaction, and gender as fixed effects, baseline (Day -1) value as the covariate with a variance-covariance matrix based on the AIC value.

Final variance-covariance matrix is XXX.

n = Number of observation used in the analysis

Least-squares means (LS Means) are calculated from the MMRM.

Group X = <description of groups>

Program: /CAXXXX/sas\_prg/pksas PROGRAMNAME.SAS DDMMYYYY HH:MM

**Note: Statistical Comparison tables 14.2.1.1.5-6.2, 14.2.1.2.5-6.2, 14.2.1.3.5-6.2, 14.2.1.4.5-6.2, 14.2.1.5.5-6.2, 14.2.1.6.5-6.2, 14.2.1.7.5-6.2, 14.2.1.8.5-6.2, 14.2.1.9.5-6.2, 14.2.1.10.5-6.2, 14.2.1.11.5-6.2, 14.2.1.12.5-6.2, 14.2.1.13.5-6.2, 14.2.1.14.5-6.2, 14.2.1.15.5-6.2, 14.2.1.16.5-6.2, 14.2.1.17.5-6.2, 14.2.1.18.5-6.2, 14.2.1.19.5-6.2, and 14.2.1.20.4-5.2 will have the following format:**

Page 1 of X  
Table 14.2.1.1.5.2 Statistical Comparisons of <Biomarker> (Units) Between Study Groups by Study Day (mITT Population)

Comparison	Study Day	----- LS Means -----	LS Mean Difference (Test - Reference)	XX% Confidence Interval	p-value
	Test (n)	Reference (n)			

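### Randomisation is stratified by gender and CPD, but the planned models adjust for gender and the outcome's baseline value and not for CPD, so standard errors may be slightly too large

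*Protocol*

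**What the plan says.** **Randomisation.** Protocol 7.5: "Groups will be stratified by gender (male or female, no more than 60% of either gender) and CPD". Protocol 3.1 and SAP 3 name the same two factors.

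**Primary model.** SAP 7.3.1: "In the model, study group, study day, and study group by study day interaction, and gender are the fixed effect factors". It continues: "The baseline value of the response biomarker is the covariate". The SAS statement matches the text: "Model response = gender group day group*day baseline/ddfm=kr".

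**Other models.**
- Secondary biomarkers, SAP 7.3.2: "The same statistical analysis model defined in the primary analysis Section 7.3.1 will also be used".
- Subjective effects, SAP 7.3.3: "Similar statistical comparison analysis (defined in 7.3.1) will be preformed on QSU-brief change from pre-use score". The mCEQ scores are handled the same way.
- Multiple-imputation analysis step, SAP 7.3.4.2: "model biomarker = gender group baseline/ddfm=kr". The preceding PROC MI step uses only the biomarker's baseline, Day 5 and Day 7 values.
- Table shells, SAP 12 (footnote of Table 14.2.1.1.5.1): "study group, study day, study group by study visit interaction, and gender as fixed effects, baseline (Day -1) value as the covariate". The multiple-imputation shell, Table 14.2.1.1.8.1, lists group, gender and baseline.
- Protocol 11.9: the ANCOVA has group, gender and baseline value or score.

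CPD is in none of these. The Use the Product Again model in Protocol 11.7 is left aside here: SAP 9 says it was modified, and the SAP specifies no replacement.

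**The concern.** A factor is normally chosen for stratification because it is expected to predict the outcome. Stratifying balances it across groups, so the between-group estimate is more precise. The analysis reports that precision only if the factor is in the model. If it is left out, its variance stays in the residual and the standard error overstates the real uncertainty. Here one stratification factor is carried into the models and the other is not, without a reason.

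What is at stake is efficiency: confidence intervals wider than necessary and tests below their nominal level. How much depends on what CPD still explains once the baseline value and gender are in the model.

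**Working it through.** The plan gives no figure on this point, so there is none to reproduce.

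**Inputs from the documents**
- Stratification factors: gender and CPD (Protocol 3.1 and 7.5, SAP 3).
- Model terms: group, day, group by day, gender, baseline (SAP 7.3.1).
- Completers needed: 35 in each of Groups 1 to 3 and 25 in each of Groups 4 to 6 (Protocol 11.2, SAP 4). Total 3 × 35 + 3 × 25 = 180.

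**Assumed input.** R² is the share of the residual variance, after baseline and gender, that one common CPD term explains. The documents do not give it. The range shown is 0, 2 and 5%.

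**Step 1: standard error.** When CPD is balanced across groups, the actual variance of the group difference is proportional to (1 − R²)σ², where σ² is the residual variance without CPD. The model without CPD uses σ². So

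reported SE / actual SE = 1/√(1 − R²).

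| Assumed R² | Calculation | SE too large by |
|---|---|---|
| 0% | 1/√1.00 = 1.000 | 0% |
| 2% | 1/√0.98 = 1.0102 | 1.0% |
| 5% | 1/√0.95 = 1.0260 | 2.6% |

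Confidence-interval width changes by the same percentages under the Dunnett adjustment, because CPD affects the critical value only through the degrees of freedom.

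**Step 2: check by simulation.** The check used a Day 5 and Day 7 repeated-measures model with 35/35/35/25/25/25 completers, two balanced CPD strata (assumed), one common CPD effect, a residual correlation of 0.7 (assumed) and 1,500 runs per value. For Group 2 against Group 1 at Day 7, the mean standard error without CPD exceeded that with CPD by 0.0, 1.1 and 2.7% (unstructured covariance), or 0.0, 1.1 and 2.6% (compound symmetry). This confirms the formula. It says nothing about which R² applies.

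**Step 3: direction of the type I error.** For one comparison at two-sided 0.025, the level assumed in Protocol 11.2, the actual level without CPD is 2 × [1 − Φ(2.2414/√(1 − R²))]. This gives 0.0250, 0.0236 and 0.0215 for R² of 0, 2 and 5%. The error rate falls below nominal and never rises above it.

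**Step 4: cost of adding CPD.** A simple count at Day 7 is 180 − 8 = 172 degrees of freedom (six group means, gender, baseline). A two-level stratum leaves 171 and a three-level stratum 170. The 95% t multiplier goes from 1.97385 at 172 to 1.97393 at 171, a rise of 0.004%. Kenward-Roger values will differ slightly from this count.

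**The case against.** The strongest defence is that the models already hold the better predictor. The Day -1 urine is collected while subjects smoke freely, and baseline CPD is the average of Days -2 and -1 (Protocol 3.1). The biomarker covariate therefore measures exposure over an overlapping period and may leave CPD almost nothing to explain. This stands for the primary endpoint and most secondary ones, and it limits the size of the gain. It does not remove the point, because the documents do not make the argument and the added term costs almost nothing. It is also weaker for questionnaire scores. For mCEQ-V there is no same-instrument baseline at all, since only mCEQ-C is given on Day -1 (SAP 7.1.4.1).

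A second defence is that protocol and SAP agree on the covariates, so this is a consistent, prespecified choice whose only possible cost is conservative tests. That stands too. A reader might infer that SAP 9 hides a departure by not mentioning CPD. It does not: section 9 lists changes from the protocol analysis, and the protocol model has no CPD term either.

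A reader might also infer a material loss of power. The documents do not support that. They give no effect size, standard deviation or baseline correlation, and the result also depends on the Dunnett adjustment. R² values above 5% are possible, but nothing in either document points to them.

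**Conclusion.** The omission is certain. Its effect is small and may be nil. A reader might take an omitted stratification factor to mean biased comparisons or too many false positives. Neither follows: stratification balances CPD across groups, and the error in the standard error is in the cautious direction.

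If CPD predicts the outcome beyond baseline and gender, standard errors and interval widths are too large by about 1.0% at R² = 2% and 2.6% at R² = 5%. If it does not, nothing is lost. These figures assume balanced CPD strata and one common CPD effect across groups. Permitted smoking differs by group, so the CPD effect may differ too, and a common term would then recover only part of it. The point is minor: a nearly free improvement to the analysis.

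**What to change.** Before data are seen:

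1. State in the SAP which CPD stratum the IWRS uses: the source of the CPD value and the cut-points. Neither document does so. Protocol 5.4 records a screening value and Protocol 3.1 defines a Day -2 and Day -1 average. Protocol 7.5 lets randomisation be completed on Day -1, when that average may not be final. The two-category split in Protocol 1.1.1.1 belongs to an earlier study.
2. Add that stratum, as used for allocation, as a fixed effect to the model in SAP 7.3.1, and so to 7.3.2 and 7.3.3.
3. In SAP 7.3.4.2, add it to the analysis model and to the PROC MI variable list (as indicator variables), so that the two steps agree on this factor.
4. Update the shell footnotes.
5. List the addition in SAP 9 as a new change from the protocol model.

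The cost is one or two of about 172 degrees of freedom and a few SAP edits. Protocol 11.1 leaves analysis details to the SAP, and SAP 9 already records a change of model, so no protocol amendment is needed. If CPD is left out on purpose, one sentence in the SAP giving the reason would settle the point.
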